5.1.2 Per-Protocol (PP) Population

[REDACTED]

5.2 Primary Endpoints

5.2.1 Primary Endpoint of Minimal Stent Area (MSA)

The primary imaging endpoint is Final Post-PCI MSA (per target lesion basis) in each randomized arm, as measured at an independent OCT core laboratory, which is blinded to imaging modality assignment.

5.2.2 Hypothesis

Let $M(\text{OCT})$ be the MSA in OCT-guided arm, while $M(\text{Angio})$ is MSA in angiography-guided arm. The following hypothesis will be tested:

$$H_0: M(\text{Angio}) - M(\text{OCT}) \geq 0$$

$$H_1: M(\text{Angio}) - M(\text{OCT}) < 0$$

The null hypothesis will be tested at the one-sided 2.5% significance level and [REDACTED]

[REDACTED]

5.2.3 Analysis Method

The mean of the MSA will be estimated in both OCT-guided and angiography-guided arm. [REDACTED]

[REDACTED]

[REDACTED]

[REDACTED]

5.2.4 Sample Size

[REDACTED]

[REDACTED]

[REDACTED] a sample size of 1600 subjects will provide at least 95% power to demonstrate superiority of treatment difference.

5.2.5 Analysis Populations

The primary endpoint of MSA will be tested in the ITT population, as defined in section 5.1 above, and for only those ITT subjects in whom one or more stents were implanted at a target lesion will be excluded from this endpoint analysis.

As a secondary analysis, the primary endpoint of MSA will be tested for the PP population as defined in section 5.1 above, and for only those PP subjects in whom one or more stents were implanted at a target lesion.

5.2.6 Poolability Analysis

[REDACTED]

Abbott

Study Name: ILUMIEN IV

Statistical Analysis Plan

[REDACTED]

5.2.7 Sensitivity Analyses

[REDACTED]

5.2.8 Subgroup Analyses

Subgroup analyses will be performed to examine the consistency of the primary endpoint of MSA across study subgroups for the following baseline variables:

- Gender: male vs. female
- Age (e.g., < 65, ≥ 65)
- Race (all categories as well as white vs non-white)
- Ethnicity (Hispanic or Latino vs not Hispanic or Latino)
- ACS vs. non-ACS
- Diabetes vs. non-diabetes
- Long or multiple lesions (defined as intended total stent length in any single target vessel ≥28 mm) vs. short and single lesions
- Bifurcations: yes vs. no
- Angiographic severe calcification vs. non-calcification
- In-stent restenosis: yes vs. no
- Medication-treated diabetes mellitus vs. others

[REDACTED]

5.3 Primary Endpoint of Target Vessel Failure

The primary clinical endpoint is the time-to-first event rate of the composite outcome of cardiac death, target vessel myocardial infarction (TV-MI) (per primary protocol definition), or ischemia-

Abbott

██████████ : ██████████ ██████████

Study Name: ILUMIEN IV

Statistical Analysis Plan

driven target vessel revascularization (ID-TVR) assessed at 2 years. For patients with multiple target vessels, TVF in either or both target vessels constitutes an endpoint event.

5.3.1 Hypothesis

The following hypothesis will be tested only in the final analysis.

$$H_0: H(\text{OCT}) / H(\text{Angio}) \geq 1$$

$$H_1: H(\text{OCT}) / H(\text{Angio}) < 1$$

where $H(\text{PCT})$ and $H(\text{Angio})$ are the hazard function for the OCT-guided arm and angiography-guided arm. The null hypothesis will be tested at the one-sided 2.5% significance level.

5.3.2 Analysis Method

The primary endpoint of TVF is defined as the time to the first TVF. ██████████

██████████
██████████
██████████
██████████
██████████

██████████
██████████

██████████
██████████ ██████████
██████████
██████████
██████████

██████████
██████████
██████████
██████████
██████████
██████████

5.3.3 Sample Size

[REDACTED]

[REDACTED] will achieve power of 90% at a one-sided significance level of 0.025. [REDACTED] approximately 2490 patients [REDACTED]

5.3.4 Analysis Populations

The primary analysis population for the primary endpoint of TVF will be the ITT population as defined in section 5.1 above.

As a secondary analysis, the primary endpoint of TVF will be tested for the PP population as defined in section 5.1 above. [REDACTED]

5.3.5 Poolability Analysis

[REDACTED]

5.3.6 Sensitivity Analysis

[REDACTED]

[Redacted text block]

5.3.7 Subgroup Analyses

Subgroup analyses will be performed to examine the consistency of primary endpoint of TVF across study subgroups for the following baseline variables:

- Gender: male vs. female
- Age (e.g., < 65, ≥ 65)
- Race (all categories as well as white vs non-white)
- Ethnicity (Hispanic or Latino vs not Hispanic or Latino)
- ACS vs. non-ACS
- Diabetes vs. non-diabetes
- Long or multiple lesions (defined as intended total stent length in any single target vessel ≥28 mm) vs. short and single lesions
- Bifurcations: yes vs. no
- Angiographic severe calcification vs. non-calcification
- In-stent restenosis: yes vs. no
- Medication-treated diabetes mellitus vs. others

[Redacted text block]

5.3.8 Additional Analyses to Assess Impact of COVID-19

[Redacted text block]

Abbott

Study Name: ILUMIEN IV

Statistical Analysis Plan

[REDACTED]

Abbott will also collect and report COVID-19 test results (positive, negative, or symptomatic and managed as COVID-19 but with no test, inconclusive test, or invalid test) using a COVID-19 Assessment Log. Additionally, protocol deviations associated with COVID-19 results will be reported.

5.4 Major Secondary Endpoint of TVF Excluding Periprocedural MI and Hypothesis

The major powered secondary endpoint is the time-to-first event rate of the composite outcome of cardiac death, target vessel-related spontaneous MI or ischemia-driven target vessel revascularization (ID-TVR), assessed at 2 years. For patients with multiple target vessels, TVF excluding periprocedural MI in either or both target vessels constitutes an endpoint event.

5.4.1 Hypothesis

The following hypothesis will be tested for the analysis on TVF excluding periprocedural MI.

$$H_0: H(\text{OCT}) / H(\text{Angio}) \geq 1$$

$$H_1: H(\text{OCT}) / H(\text{Angio}) < 1$$

where $H(\text{OCT})$ and $H(\text{Angio})$ are hazard function for the OCT-guided arm and angiography-guided arm. The null hypothesis will be tested at the one-sided 2.5% significance level.

5.4.2 Analysis Methodology

[REDACTED]

Abbott

[REDACTED] : [REDACTED] [REDACTED]

Study Name: ILUMIEN IV

Statistical Analysis Plan

[REDACTED]
[REDACTED]
[REDACTED]

5.4.3 Sample Size

[REDACTED]
[REDACTED]
[REDACTED]
[REDACTED]
[REDACTED]
[REDACTED]

5.4.4 Analysis Population

The major secondary endpoint analysis population will be the ITT population as defined in section 5.1 above.

As a secondary analysis, the major secondary endpoint will be tested for the PP population as defined in section 5.1 above. [REDACTED]
[REDACTED]

5.4.5 Poolability Analysis

[REDACTED]
[REDACTED] | [REDACTED]
[REDACTED]
[REDACTED]
[REDACTED]
[REDACTED]
[REDACTED]

5.4.6 Sensitivity Analysis

[REDACTED]
[REDACTED]
[REDACTED]
[REDACTED]
[REDACTED]
[REDACTED]

Abbott

Study Name: ILUMIEN IV

Statistical Analysis Plan

[REDACTED]

5.4.7 Subgroup Analyses

Subgroup analyses will be performed to examine the consistency of the major secondary endpoint across study subgroups for the following baseline variables:

- Gender: male vs. female
- Age (e.g., < 65, ≥ 65)
- Race (all categories as well as white vs non-white)
- Ethnicity (Hispanic or Latino vs not Hispanic or Latino)
- ACS vs. non-ACS
- Diabetes vs. non-diabetes
- Long or multiple lesions (defined as intended total stent length in any single target vessel ≥28 mm) vs. short and single lesions
- Bifurcations: yes vs. no
- Angiographic severe calcification vs. non-calcification
- In-stent restenosis: yes vs. no
- Medication-treated diabetes mellitus vs. others

[REDACTED]

5.4.8 Additional Analyses to Assess Impact of COVID-19

[REDACTED]

5.5 Secondary Endpoints

Descriptive endpoints are reported using only summary statistics and no hypothesis test will be performed.

Procedural outcomes

OCT-defined (OCT core laboratory assessed). Subjects in the angiography-guided arm will

undergo a post-PCI OCT run, blinded to the operator. Assessed per target lesion.

- 1) Stent expansion. Stent expansion is defined by the MSA achieved in the proximal and distal stented segments relative to their respective reference lumen areas. The stent length is divided into 2 equal segments (proximal and distal) except for lesions containing a bifurcation (visually estimated side branch ≥ 2.5 mm). When there is a bifurcation present, rather than splitting the stent into two halves, the division occurs at the proximal most side branch.
 - Acceptable stent expansion (categorical variable): The MSA of the proximal segment is $\geq 90\%$ of the proximal reference lumen area and the MSA of the distal segment is $\geq 90\%$ of the distal reference lumen area.
 - Unacceptable stent expansion (categorical variable): The MSA of the proximal segment is $< 90\%$ of the proximal reference lumen area, and/or the MSA of the distal segment is $< 90\%$ of the distal reference lumen area.

In case either segment (proximal or distal) of the stent meets criteria for unacceptable stent expansion, the stent is considered to have unacceptable stent expansion. Both segments of the stent must meet acceptable stent expansion criteria to be considered acceptable.

In case a respective reference segment cannot be measured the determination will be made with only one of the two reference (proximal or distal) segments.

Note: If acceptable stent expansion (by operator assessment) is not achieved in either the distal or proximal segments of the stent in the OCT-guided arm according to the Post-PCI OCT, further post-stent expansion with higher pressures and/or larger balloons must be performed per protocol if the POST-PCI OCT EEL measurements now suggest a larger balloon be used. See CIP Section 6.5.3.7 for more details.

- Post-PCI stent expansion (%) (continuous variable): The MSA divided by the average of proximal and distal reference lumen areas x 100.
- 2) Mean stent expansion (%) (continuous variable): The mean stent area (stent volume/analysed stent length) divided by the average of proximal and distal reference lumen areas x 100.
 - 3) Intra-stent plaque protrusion and thrombus

Defined as a mass attached to the luminal surface or floating within the lumen, meeting the following criteria: Protrusion/thrombus is defined as any intraluminal mass protruding at least 0.2 mm within the luminal edge of a stent strut, and will be further classified as Major and Minor:

- Major: Protrusion area/Stent area at site of tissue protrusion $\geq 10\%$ and the minimal intrastent flow area (MSA – protrusion area) is unacceptable ($< 90\%$ of respective proximal or distal reference area)
- Minor: Protrusion area/Stent area at site of tissue protrusion is $< 10\%$, or is $\geq 10\%$ but the minimal intraluminal flow area (MSA – protrusion area) is acceptable ($\geq 90\%$ of respective proximal or distal reference area)

Note: It is recommended that if protrusion is detected by operator assessment in the OCT-guided arm during the procedure and meets the criteria for major protrusion, then thrombus aspiration, further high-pressure balloon inflation and/or an additional stent be considered.

4) Untreated reference segment disease

Defined as focal disease with untreated MLA $< 4.5 \text{ mm}^2$ within 5 mm from the proximal and/or distal stent edges.

Sub-classified by the amount of untreated lipid plaque, divided into 3 grades:

- i. Low ($\leq 90^\circ$ of lipid arc)
- ii. Medium ($> 90^\circ - < 180^\circ$ of lipid arc)
- iii. High ($\geq 180^\circ$ of lipid arc)

Note: If untreated reference segment disease with an MLA $< 4.5 \text{ mm}^2$ is detected by operator assessment in either the proximal reference (inflow disease) or distal reference (outflow disease) segment lumen in the OCT-guided arm, an additional stent must be placed to treat it, unless there are anatomic reasons that the disease should not be covered (e.g. diffuse distal disease or significant vessel tapering, etc.)

5) Edge dissections

Edge dissections will be tabulated as:

- i. Major (%): ≥ 60 degrees of the circumference of the vessel at site of dissection and ≥ 3 mm in length
- ii. Minor (%): any visible edge dissection < 60 degrees of the circumference of the vessel or < 3 mm in length

Edge dissections will be further classified as:

- i. Intimal (limited to the intima layer, i.e. not extending beyond the internal elastic lamina)
- ii. Medial (extending into the media layer)
- iii. Adventitial (extending through the external elastic membrane/lamina)

Note: If a major edge dissection is detected by operator assessment in the OCT-guided arm, it is recommended that an additional stent be placed to cover the dissected segment, particularly if the site of dissection is at the distal stent edge.

6) Stent Malapposition

Defined as frequency (%) of incompletely apposed stent struts (defined as stent struts clearly separated from the vessel wall (lumen border/plaque surface) without any tissue behind the struts with a distance from the adjacent intima of ≥ 0.2 mm and not associated with any side branch).

Malapposition will be further classified as:

- Major: if associated with unacceptable stent expansion (as defined above)
- Minor: if associated with acceptable stent expansion (as defined above)

Note: If malapposition is detected by operator assessment during the procedure in the OCT-guided arm and meets the criteria for major malapposition (i.e. malapposition associated with unacceptable stent expansion), further stent expansion must be performed. The degree of stent underexpansion (acceptable or unacceptable) should guide the intervention rather than amount of malapposition.

Stent Malapposition will be tabulated as:

- i. Major (%)
 - ii. Minor (%)
 - iii. All (Major and Minor) (%)
- 7) Border detection (angiography arm post-PCI only, blinded to investigator)

The visibility of the vessel external elastic lamina (EEL) border by OCT will be evaluated at both reference sites (proximal and distal) and the MSA, after intervention and then classified into 3 grades:

 - i. Good: $\geq 75\%$ (270°) of visible circumference
 - ii. Moderate: $\geq 50\%$ (180°) - $< 75\%$ (270°) of visible circumference
 - iii. Poor: $< 50\%$ (180°) of visible circumference
- 8) Intra-stent lumen area (intra-stent flow area)

Defined as stent area minus any protrusion as defined above in secondary endpoint 3 (Intra-stent plaque protrusion and thrombus).
- 9) Effective lumen area (total flow area)

Defined as intra-stent lumen area plus any area of malapposition between the stent and the vessel wall (lumen border/plaque border).
- Additional Procedural Endpoints**
- 10) Angiographic Endpoints (QCA). (Angiographic core laboratory assessed). Assessed per target lesion.
 - i. Final (post-PCI) minimal lumen diameter
 - ii. Final (post-PCI) percent diameter stenosis
 - iii. Acute lumen gain post-intervention
 - iv. Maximum device size (stent or post-dilatation balloon)/reference vessel diameter ratio

- v. Post-PCI target vessel TIMI flow rate
 - vi. Angiographic complications – worst (anytime during the procedure) and final (post PCI and all imaging) - Angiographic dissection \geq NHLBI type B, perforations (Ellis classification), intra-procedural thrombotic events (including slow-flow, no-reflow, side branch closure, distal embolization, and intra-procedural stent thrombosis, as per the standard angiographic core laboratory definitions
- 11) Device Usage Endpoints (site reported; assessed per subject):
- i. Total stent length
 - ii. Total number of stents
 - iii. Maximal stent size
 - iv. Post dilatation (yes/no)
 - v. Total number of post-dilation balloons
 - vi. Maximal post-dilatation balloon size
 - vii. Maximal device size (stent or post-dilatation balloon)
 - viii. Maximum inflation pressure (atm.; stent or post-dilatation balloon)
- 12) Procedure time (first angiogram to guide catheter removal), fluoroscopy time, radiation exposure
- 13) Contrast use; contrast induced nephropathy (defined as serum creatinine rise $>25\%$ or absolute increase >0.5 mg/dL ($44.2\mu\text{mol/L}$)); need for renal replacement therapy
- 14) Procedural success (must be present in all treated lesions and vessels):
- Defined as A) angiographic core laboratory-assessed final (post-PCI) lesion angiographic diameter stenosis $<30\%$ and target vessel TIMI III flow without any of the angiographic complications listed in 10(vi) above; plus B) the absence of site-assessed prolonged ST-segment elevation or depression (>30 minutes), cardiac arrest or need for defibrillation or cardioversion or hypotension/heart failure requiring mechanical or intravenous hemodynamic support or intubation, or procedural death.

Abbott

Study Name: ILUMIEN IV

Statistical Analysis Plan

15) Procedural complications

Defined as A) angiographic core laboratory-assessed complications listed in 10(vi) above occurring anytime during the procedure; or B) site-assessed prolonged ST-segment elevation or depression (>30 minutes), cardiac arrest or need for defibrillation or cardioversion or hypotension/heart failure requiring mechanical or intravenous hemodynamic support or intubation, or procedural death.

16) OCT performance success (site reported) (OCT arm only):

OCT imaging performed both pre- and post-PCI

17) OCT imaging-related procedural complications (CEC adjudicated)

Any procedural complications (e.g. angiographic dissection, perforation, thrombus, acute closure, etc.) requiring any active intervention (e.g. prolonged balloon inflations, additional stent implantation, pericardiocentesis, intubation, hemodynamic support or pressors, defibrillation or cardioversion) or death adjudicated by the CEC as definitely or likely attributable to the physical performance of OCT-imaging (e.g. passing the catheter through the vasculature or stent, or injecting contrast to clear the blood for imaging). For this definition, adverse events that arise due to changes in PCI strategy as the result of OCT findings are NOT considered OCT imaging-related procedural complications.

18) Additional interventions on the basis of the pre-PCI or post-stent OCT-imaging run that would not have been performed based on angiographic guidance alone (site reported; assessed per subject; OCT Arm Only):

- i. Use of larger balloon
- ii. Use of higher inflation pressures
- iii. Use of additional balloons
- iv. Use of additional stent(s)
- v. Performance of atherectomy
- vi. Other interventions

Reason(s) for additional interventions will be documented by the site (e.g. more calcium

Abbott

Study Name: ILUMIEN IV

Statistical Analysis Plan

than anticipated, greater stent under-expansion than appreciated angiographically, greater malapposition than appreciated angiographically, greater tissue protrusion or thrombus burden than appreciated angiographically, more severe edge dissection than appreciated angiographically, residual reference segment disease not appreciated angiographically, other)

Clinical outcomes at 30 days, 1 year, and 2 years (unless otherwise noted)

- 19) Target lesion failure (TLF; cardiac death, TV-MI or ischemia-driven target lesion revascularization (ID-TLR)
- 20) All-cause mortality
- 21) Cardiac and non-cardiac mortality
- 22) All MI
- 23) TV-MI, non-TV-MI and indeterminate vessel MI
- 24) Periprocedural MI and non-periprocedural MI
- 25) All revascularization
- 26) ID-revascularization and non-ID-revascularization
- 27) ID-TVR, ID-TLR, ID-non-TLR TVR, and ID-non-TVR
- 28) Definite, probable and definite/procedure stent thrombosis (ARC definition)
- 29) Relationship between immediate post-procedure OCT parameters (e.g. MSA, procedural success, malapposition, dissection, protrusion, etc.) and 2-year endpoint rates (e.g. TVF, TLF, all-cause mortality, cardiac death, TV-MI, all MI, ID-TLR, ID-TVR, and stent thrombosis)
- 30) TVF excluding periprocedural MI (i.e. the composite of cardiac death, target vessel-related spontaneous MI, or ID-TVR) (at 30 days and 1 year)

In addition, the following outcomes using the SCAI definition of periprocedural MI will be reported as sensitivity analyses at 30 days, 1 year and 2 years:

Abbott

Study Name: ILUMIEN IV

Statistical Analysis Plan

- 31) TV-MI_{SCAI} (periprocedural MI by SCAI definition and spontaneous MI by protocol definition)
- 32) Periprocedural MI_{SCAI} (by SCAI definition)
- 33) All MI_{SCAI} (periprocedural MI by SCAI definition and spontaneous MI by protocol definition)
- 34) TVF_{SCAI}; the composite of cardiac death, TV-MI_{SCAI} or ID-TVR

Patient Reported Outcomes (PRO)

Patient Reported Outcome questionnaires will be incorporated into this study to provide a complementary evaluation of the effectiveness of OCT-guided stent implantation. The following instruments will be administered during this study at baseline (optional post-procedure), 30 day, 12 month and 24 month follow-up:

- EuroQoL 5D (EQ-5D-5L) survey to assess overall health status

5.5.1 Analysis Method

Analyses of all secondary endpoints will be performed according to their randomized group regardless of the device attempted or implanted. All continuous secondary endpoints will be summarized descriptively by number of observations available, mean, standard deviation, median, minimum, maximum; categorical secondary endpoints will be summarized by, the number within each category and the percentage out of the total number of available observations for each randomized arm and overall subjects.

Procedural outcome and Additional Procedural Endpoints

For continuous endpoints, the summary statistics will be presented by randomized arm. Changes from baseline to follow-up, where applicable, will be assessed by ANCOVA, adjusting for the baseline measurement in each group, and least square means, differences thereof and 95% CI of the differences will be reported.

For categorical endpoints, the percentages of each category will be presented by randomized arm and compared using a 95% confidence interval for the difference.

Clinical outcomes

The endpoints will be summarized via Kaplan Meier estimates and a Kaplan-Meier plot. The following statistics will be reported at 1 year and 2 years: estimated event rates and its 95% confidence interval (CI), log-rank p-value, and hazard ratios with 95% Wald CI's obtained via Cox proportional hazards regression.

Abbott

Study Name: ILUMIEN IV

Statistical Analysis Plan

Relationship between immediate post-procedure OCT parameters and 2-year endpoint rates will be explored using univariate and Cox multiple regression.

Patient Reported Outcomes (PRO)

The end point of PRO will be summarized by randomized arm. [REDACTED]

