### 6.5.2 Randomization

Target lesions will be identified based on coronary angiography (plus use of physiological assessment of coronary artery disease as appropriate) for eligibility for PCI. If all inclusion criteria are present and no exclusion criteria are present for at least one target lesion, the patient may be randomized. Randomization should be performed immediately following angiography, or after successful and uncomplicated PCI of one or more lesions in a non-randomized non-target vessel. Randomization is performed before wire crossing or PCI on any lesion in a target vessel is performed with a few exceptions. The lesion may be crossed with a pressure wire to determine its physiological significance and for randomized CTO lesions, for which randomization will occur after successful antegrade wire crossing and successful pre-dilatation with confirmation that the culprit lesion is amenable to OCT-guidance. If the CTO is not successfully crossed with antegrade wire escalation techniques and non successfully pre-dilated, or if complications occur during the CTO recanalization procedure, the patient may not be randomized.

Randomization will be stratified by medication-treated diabetes, presentation with a biomarker positive ACS (NSTEMI or recent STEMI), and site. Randomization allocation will be through an electronic randomization system. A cap of 10% will be implemented for in-stent restenosis in the overall population (see **Section 5.4.1**, Inclusion Criteria #3.B.vi). Prior to randomization the site will declare to the electronic randomization system the stratification variables. Designation of planned staging may be modified within 24 hours after the procedure if necessary (see **Section 6.5.3.8** for more details). The intent to stage will be used by the CEC in determining whether subsequent revascularization procedures are unplanned, thus meeting the criteria for endpoint events. However, even planned staged interventions may be included as an endpoint event if done urgently and sooner than planned for active ischemia.

Note: Each target vessel may contain up to two target lesions, and there may be up to 2 randomized target vessels (i.e. up to 4 target lesions). All lesions in target vessels must be determined by the operator to be amenable to OCT-guided PCI, although only one of the lesions must have high-risk angiographic characteristics.

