#### 7.1.2.2 Sample Size Determination

[REDACTED] will provide 90% power at a one-sided significance level of 0.025, which is associated with approximately 2490 subjects. If an interim analysis indicates a sample size increase, the enrollment can be adjusted up to a total of 3656 subjects.

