3.0 TRIAL DESIGN

This is a prospective, single-blind clinical investigation randomizing subjects to OCT-guided coronary stent implantation vs. angiography-guided coronary stent implantation in a 1:1 ratio. The clinical investigation will be conducted at approximately 125 centers in North America (US and Canada), Western Europe, and Asia-Pacific. Up to 3656 randomized subjects and approximately 375 roll-in subjects will be enrolled in the clinical investigation. No site may enroll more than 15% of the total subjects. Subjects participating in this clinical investigation will be followed for 2 years. The expected duration of enrollment is approximately 2 years. The total duration of the clinical investigation is expected to be approximately 5 years.

The sample size is driven by the primary endpoint of target vessel failure (TVF). Because of the event driven nature of this primary endpoint, the statistical power of the trial is a function of the number of endpoint events, and not a direct function of the number of patients enrolled. As a result, the number of patients is not an endorsement of the statistical power of the trial. If event rates are lower than anticipated, more patients will be required to obtain a sufficient number of endpoint events.

Subjects will be randomized in a 1:1 ratio according to an electronic randomization system. Randomization will be stratified by medically treated diabetes, presentation with a biomarker positive ACS (NSTEMI or recent STEMI), and site.

Each operator will complete OCT-guided stenting roll-in cases (up to 3, if needed) according to a pre-specified stent optimization protocol on patients meeting study inclusion/exclusion criteria. Within 72 hours of receipt, the core lab will determine accurate OCT measurements and stent optimization protocol compliance. OCT Core laboratory approval of each operator is required to proceed to the randomization phase.

Subjects will be considered enrolled in the trial once informed consent has been obtained and the subject is randomized. The trial will utilize a Clinical Events Committee (CEC) to review adverse events for adjudication of trial endpoints.

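### The visible methods in SAP 5.5.1 for the non-powered secondary endpoints leave out the randomization factors, so difference-scale intervals are valid but somewhat wider than needed

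*SAP*

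**What the plan says.** Both documents describe the same allocation scheme. SAP 3.0 states: "Randomization will be stratified by medically treated diabetes, presentation with a biomarker positive ACS (NSTEMI or recent STEMI), and site". Protocol 6.5.2 names the same three factors and has the site declare them to the electronic system before randomization. SAP 3.0 also says: "The clinical investigation will be conducted at approximately 125 centers".

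SAP 5.5.1 then gives readable methods for the non-powered secondary endpoints:

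- Continuous procedural endpoints: summary statistics by arm. Only changes from baseline, where they exist, get a between-arm comparison, and these "will be assessed by ANCOVA, adjusting for the baseline measurement in each group".
- Categorical procedural endpoints: percentages by arm, with a 95% interval for the difference.
- Clinical outcomes: Kaplan-Meier estimates, a log-rank p-value, and "hazard ratios with 95% Wald CI's obtained via Cox proportional hazards regression".

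None of this text names diabetes, ACS or site as a stratum or covariate. SAP 5.5 calls these endpoints descriptive and rules out hypothesis tests. The methods for both primary endpoints, the major secondary endpoint and the patient-reported outcome are wholly or partly redacted.

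**The concern.** When allocation is balanced within strata, differences between strata largely cancel out of the true sampling variance of a difference in means or proportions. An analysis that ignores the strata still counts that variation in its standard error. Its interval is then wider than the design warrants and its coverage is at or above nominal.

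Site is the factor most likely to matter for procedural endpoints. Protocol 6.5.3.2 leaves angiography-guided stenting to local standard practice, so variation between sites is plausible, although neither document quantifies it. What is at stake is precision that the trial has already paid for by stratifying. No false claim of benefit can arise from the omission.

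**Working it through.** **The plan's own figure.** The documents state no interval width or precision target for these endpoints. The nearest figure is for TVF, where Protocol 7.1.2.2 says a redacted quantity "will provide 90% power at a one-sided significance level of 0.025, which is associated with approximately 2490 subjects". The hazard ratio, event rate and event count are redacted, so 2490 can be neither reproduced nor refuted. With Schoenfeld's formula, events = 4(1.960 + 1.282)² / (ln HR)². Hazard ratios of 0.60, 0.65, 0.70 and 0.75 need 162, 227, 331 and 508 events, or 6.5%, 9.1%, 13.3% and 20.4% of 2490. Many input pairs fit. I use 2490 only as the size for the checks below.

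**Differences in means.** With 1:1 allocation the unadjusted variance is 4σ²/N. Adjusting for factors that explain a share R² of the variance gives 4σ²(1 - R²)/N, so the width ratio is sqrt(1 - R²). For ANCOVA, R² is the share of the variance left after the baseline value.

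This was compared with a simulation using N = 2490, 125 unequal sites, and permuted blocks of 4 within diabetes x ACS x site. It ran 3000 trials per row, with site as a fixed effect. Block size, prevalences (diabetes 40%, ACS 30%), site sizes and site variance are assumptions.

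| Site share of variance | 1 - sqrt(1 - R²) | Simulated narrowing | Unadjusted 95% interval excludes a true zero |
|---|---|---|---|
| 5% | 2.5% | 1.7% | 5.4% |
| 10% | 5.1% | 4.4% | 4.5% |
| 20% | 10.6% | 9.7% | 2.9% |
| 30% | 16.3% | 15.5% | 2.4% |

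The adjusted interval excluded a true zero in 4.8% to 5.7% of trials throughout. Incomplete blocks and unequal sites reduce the gain only slightly.

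**Differences in percentages.** A simulation of the same size, with site, diabetes and ACS entered additively in a linear model, gave intervals about 1% to 8% narrower. By the same formula this corresponds to explained shares of 1 - 0.99² = 2% to 1 - 0.92² = 15%. With diabetes and ACS alone the gain was under 0.5%.

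A separate set of 1000 trials per scenario used Mantel-Haenszel risk differences, with assumed control rates of 3% or 12%. Relative to the unstratified interval, width changed by -0.06% to -1.6% with diabetes x ACS strata. With all three factors fully crossed it changed by -1.0% to +2.6%. Two things explain the poor showing of full crossing:

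- There are up to 125 x 2 x 2 = 500 strata, or 2490/500 ≈ 5 subjects each.
- Site explains little of a less common binary outcome. If the site log-hazard SD is s and the rate is p, its share is roughly (p·s)²/[p(1 - p)]. That is 0.036²/0.1056 = 1.2% at p = 0.12, s = 0.3, and 0.009²/0.0291 = 0.3% at p = 0.03.

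**Cox intervals.** The standard error of the log hazard ratio is governed by the number of events (about 2/sqrt(events) at 1:1), and a covariate does not change that number. Assumptions: HR 0.70; control rate 3% or 12%; diabetes HR 1.5 to 2.5; ACS HR 1.3 to 2.0; site SD 0.3 to 0.5.

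| Analysis | Change in width | Mean SE, moderate case | Mean SE, strong case |
|---|---|---|---|
| Unadjusted | reference | 0.1291 | 0.1311 |
| Adjusted for diabetes + ACS | +0.01% to +0.02% | 0.1291 | 0.1311 |
| Stratified, diabetes x ACS | +0.02% to +0.03% | 0.1292 | 0.1311 |
| Stratified, diabetes x ACS x site | +4.3% to +6.2% | 0.1352 | 0.1392 |

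Coverage of the unadjusted interval was 95.4% to 96.3%. In the strong case the mean log hazard ratio was -0.350 unadjusted and -0.356 adjusted, against a conditional true value of ln 0.70 = -0.357. The share of trials with z < -1.96 rose from 76.4% to 78.1%. In the moderate case it hardly moved (80.2%, against 80.1% adjusted and 80.4% stratified).

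**The case against.** The strongest reply is that little depends on this. The endpoints are descriptive, carry no success criterion, and have intervals that are valid to slightly conservative. That stands, and it fixes the severity as minor. It does not make the omission a matter of style: SAP 5.5.1 does report between-arm intervals and a log-rank p-value, readers will use them, and the adjustment is free.

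A reader might infer more than the documents support:

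- **That the Cox intervals are too wide.** They are not. Adjustment leaves them unchanged, and adding site as a stratum widens them.
- **That procedure time, fluoroscopy, contrast use and device use lose most.** SAP 5.5.1 plans only summary statistics by arm for such single procedural values, so there is no planned interval to narrow.
- **That the primary, major secondary or patient-reported analyses ignore the strata.** Those methods are redacted and cannot be judged. Blacked-out text may handle the strata.
- **That strong variation between sites is established.** No site variance appears in either document; every share above is assumed.

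It is also fair to object that about 125 site effects are unsuitable for uncommon binary outcomes. That stands and shapes the fix.

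**Conclusion.** The omission is real within the visible text of SAP 5.5.1, and its effect is modest and confined. It touches two planned comparisons: ANCOVA of changes and intervals for differences in percentages. If site explains 5% to 30% of variance, intervals for continuous changes could be about 2% to 15% narrower. Those for common binary procedural endpoints could be about 1% to 8% narrower, and for rare outcomes the gain is negligible. Unadjusted intervals are valid to slightly conservative.

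For log-rank and Cox, stratifying by diabetes and ACS aligns the analysis with the randomization and gives at most a small gain in power. It also makes the hazard ratio conditional on the strata, which the SAP should state. Mean and risk differences keep the same meaning after linear adjustment. All sizes rest on the assumed site variance, block size and prevalences.

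**What to change.** In SAP 5.5.1:

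1. Add medication-treated diabetes, biomarker-positive ACS and site (random or fixed effect) to the ANCOVA models for changes.
2. Compute differences in percentages adjusted for diabetes, ACS and site, entered additively and not as fully crossed strata. Use diabetes x ACS only when the outcome is rare, with the threshold set in advance.
3. Stratify the log-rank and Cox analyses by diabetes and ACS, not by site, and say that the hazard ratio is conditional on those strata.
4. State that the values declared at randomization define the factors.

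The cost is SAP wording and minor programming. The factors are already held in the randomization system, so no new data are needed, and sample size and conduct are unaffected. The change should be made before the arms are compared.
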